12.2.8 SAFETY ANALYSES

Safety analysis will use the Safety Population. The overall safety and tolerability of BTRX-246040 treatment will be assessed by evaluating the safety and tolerability measures listed below.

For continuous variables, descriptive statistics (n, mean, SD, median, minimum, and maximum) will be provided for actual values and changes from baseline to each time point. For categorical

variables, subject counts and percentages will be provided. Summaries will be presented by treatment group.

12.2.8.1 ADVERSE EVENTS

Adverse events will be recorded from the time when a subject has signed the ICF through the Follow-Up period. The MedDRA dictionary will be used to standardize the terms used by the Investigator to describe the AEs. Adverse event analyses will include TEAEs, defined as AEs which start after the first dose of the study medication. The TEAEs will be summarized as subject and event counts, complemented by percentages calculated for the subject count, unless specified otherwise. At least the following analyses of TEAEs will be provided.

- Breakdown of TEAEs by System Organ Class (SOC) and preferred term, according to MedDRA dictionary.
- Breakdown of TEAEs by SOC, preferred term, and severity (event count only, percentages calculated out of the total number of TEAEs)
- Breakdown of TEAEs by SOC, preferred term, and relationship to the study medication (event count only, percentages calculated out of the total number of TEAEs)
- Breakdown of TEAEs leading to death by SOC and preferred term
- Breakdown of Serious TEAEs other than deaths by SOC and preferred term
- Breakdown of AEs leading to premature discontinuation by SOC and preferred term
- Listings of non-TEAEs will also be provided.

In case the number of TEAEs in the tabulations above is low, the tabulations will be replaced by data listings.

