10.2.1 ADVERSE EVENTS

An AE is any sign, symptom, illness, clinically significant abnormal laboratory value or ECG finding, or other untoward medical occurrence associated with the use of an investigational product that appears or worsens in a subject during a clinical study. This definition does not imply a causal relationship between the AE and the investigational product.

Adverse events beginning with the initial dose of investigational product or during the subsequent duration of their enrollment in the study will be considered treatment-emergent AEs (TEAE). TEAEs will be recorded on the AE CRF to include the event, date of onset, severity, frequency, seriousness, date of resolution, action taken with respect to the AE (e.g., concomitant medication, non-pharmacological treatment, etc.), outcome, and relationship to the investigational product. All TEAEs related to study drug will be followed through resolution or 30 days after the subject terminates from the study, whichever occurs first.

Medical conditions present or AEs occurring prior to the first dose of investigational product will be captured as medical history in the CRF. Any AE occurring during the study that is related to a pre-existing condition or event that worsens in intensity or frequency after the first dose of investigational product will be recorded as a TEAE.

Lack of drug effect is not an AE in clinical studies because the purpose of the clinical study is to establish drug effect.

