10.2.2 CLASSIFICATION OF AN ADVERSE EVENT

10.2.2.1 SEVERITY OF EVENT

Each AE will be assessed by the Investigator with regard to the categories discussed in the sections below. The Investigator will assess all AEs for severity in accordance with the following standard ratings.

MILD = of little concern to the subject and/or of no clinical significance; is not expected to have any effect on the subject's health or well-being;

MODERATE = discomfort enough to cause interference with or change in usual activities; is likely to require medical intervention and/or close follow-up;

SEVERE = incapacitating or unable to work or participate in many or all usual activities, is of concern to the subject and/or poses substantial risk to the subject's health or well-being; is likely to require medical intervention and/or close follow-up.

For an AE that begins and ends on the same day and severity worsens over that day, one AE will be recorded and will be assessed with the highest level of severity for that day. For an AE that continues over multiple days (past the initial day of onset), if an increase in severity level occurs, only the maximum level of severity will be documented. For a non-TEAE in which the duration continues beyond administration of the first dose of study drug, if the AE increases in severity or frequency after study drug administration, then the initial AE will be closed and a new TEAE

will be opened documenting the new higher level of severity (at the maximum severity level for the remaining duration of the AE). An AE characterized as intermittent requires documentation of onset and duration of each episode.

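### The TEAE severity and relationship tables in section 12.2.8.1 count events only, so no listed table gives the number of subjects with a severe or a related TEAE

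*Protocol*

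**What the plan says.** Section 12.2.8.1 of the protocol opens its TEAE analysis with a general rule: "The TEAEs will be summarized as subject and event counts, complemented by percentages calculated for the subject count, unless specified otherwise". A list of minimum analyses follows. Two entries on it depart from the rule. The severity table is "Breakdown of TEAEs by SOC, preferred term, and severity (event count only, percentages calculated out of the total number of TEAEs", and the other is the table by "relationship to the study medication (event count only, percentages calculated out of the total number of TEAEs". The remaining breakdowns (all TEAEs by system organ class and preferred term, TEAEs leading to death, other serious TEAEs, AEs leading to discontinuation) carry no such restriction and so keep the default.

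The section closes with a fallback: "In case the number of TEAEs in the tabulations above is low, the tabulations will be replaced by data listings". It gives no threshold for a low number.

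The parent section, 12.2.8, sets subject counts and percentages as the rule for categorical safety variables and adds: "Summaries will be presented by treatment group". Section 12.2.1 has eCRF data listed by treatment group and subject.

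**The concern.** Section 5.1 puts safety and tolerability first among the objectives, and the design compares ascending doses with 6 active subjects each. The natural questions at each dose are how many subjects had a severe TEAE and how many had one judged related. The two tables that address severity and relationship are the two from which the protocol removes the subject count.

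Events within one subject are not independent, so an event count cannot stand in for a count of affected subjects. The denominator is also a number of events. It changes with how many other TEAEs occur, including mild ones, and says nothing about how many people were exposed. At stake is how clearly severity and relationship by dose can be read from the summary tables.

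**Working it through.** The plan gives no figure to reproduce here: there is no formal sample size calculation and no assumed event rate. The check compares the listed tables and then does arithmetic on assumed event counts.

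**Inputs**
- Three cohorts of 8, randomized 6:2 (section 6.1), so 6 active subjects per planned dose.
- Counting rules from section 12.2.8.1.
- All event counts below are assumptions for illustration.

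**Step 1: what each listed table prints**

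| Table in 12.2.8.1 | Subject count | Split by severity | Split by relationship |
|---|---|---|---|
| TEAEs by SOC and preferred term | yes (default) | no | no |
| TEAEs by severity | no | yes | no |
| TEAEs by relationship | no | no | yes |
| TEAEs leading to death | yes (default) | no | no |
| Other serious TEAEs | yes (default) | no | no |
| AEs leading to discontinuation | yes (default) | no | no |

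No row combines a subject count with severity or with relationship.

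**Step 2: what an event count leaves open.** If a dose group of 6 has k severe events, the number of affected subjects lies between 1 and min(k, 6).
- k = 3: 1/6 = 16.7% to 3/6 = 50.0%.
- k = 5: 1/6 = 16.7% to 5/6 = 83.3%.
- k = 6: 1/6 = 16.7% to 6/6 = 100%.

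**Step 3: what the preferred-term table resolves.** That table keeps subject counts, so it narrows the range within a single preferred term. Take three severe events under one term.
- If 1 subject had the term, all three events are that subject's.
- If 2 subjects had it, at most 2 are affected.
- For the full range of 1 to 3 to stay open, at least three subjects must have the term. One of them could then hold all three severe events only if each of the other two has a non-severe one, so there must be at least 3 + 2 = 5 events.

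Across terms the table does not settle the matter. Suppose three severe events fall under three preferred terms in different system organ classes, each showing 1 subject and 1 event. They may belong to one subject (1/6 = 16.7%) or to three (3/6 = 50.0%), and both tables print the same either way.

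**Step 4: what the percentage means.** Event percentage = severe events / total TEAEs. Subject percentage = subjects with a severe TEAE / subjects dosed. Let 2 of 6 subjects have one severe event each.
- Total of 10 TEAEs: 2/10 = 20.0%.
- Total of 3 TEAEs: 2/3 = 66.7%.
- By subject, in both cases: 2/6 = 33.3%.

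The same two subjects give 20.0% or 66.7%, depending only on how many other events were reported. The text does not say whether the total is per group or overall. Either way the denominator is a number of events.

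**The case against.** The strongest reply is that nothing is lost. Section 12.2.1 provides listings by treatment group and subject, and severity and relationship are recorded for each TEAE. With 6 active subjects per dose, a single administration and follow-up to about Day 8, affected subjects can be counted by hand. If TEAEs are few, listings replace the tables altogether. The list of analyses is a stated minimum, so the statistical analysis plan, which is not shown, may add a subject-level row without conflict. All of this stands, and it sets the weight of the point. It does not change what these two tables are specified to print, and the protocol does not require the additional row.

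A reader might go further in four ways that the documents do not support.
- **That 12.2.8.1 contradicts itself.** It does not. The default expressly allows exceptions, and these are two of them.
- **That dose escalation is affected.** Sections 9.7 and 10.5.8 have the Dosing Review Committee review unblinded data and do not tie its decisions to these tables.
- **That repeated episodes inflate the denominator.** Section 10.2.2.1 says "An AE characterized as intermittent requires documentation of onset and duration of each episode". That asks for documentation and does not make each episode a separate TEAE. Section 10.2.1 records frequency as an attribute of the event.
- **That tolerability would otherwise go unreported.** Disposition (12.2.3), reasons for early discontinuation (7.3.1) and the table of AEs leading to discontinuation already cover it.

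**Conclusion.** The point holds as a minor one. Section 12.2.8.1 fixes a counting unit and a denominator for the severity and relationship tables that cannot show how many subjects per dose had a severe or a related TEAE, and no other listed table supplies that number. Three severe events summed across preferred terms in a group of 6 are compatible with 17% to 50% of subjects. This range rests on the planned 6 active subjects per dose and on an assumed event count. It is widest across preferred terms and narrower within one. The conclusion concerns the tables that the protocol lists. It does not claim that the final report will lack the information, which remains recoverable from the listings.

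**What to change.** In section 12.2.8.1, replace the parenthesis in both the severity and the relationship bullet with wording such as: *number and percent of Safety Population subjects per dose group and placebo, each counted once at worst severity [closest relationship], denominator = subjects dosed, with event counts beside*. This restores the section's own default and keeps the event counts.

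The cost is two edited parentheses and slightly more table work. No new data are needed. Section 10.2.1 states that "TEAEs will be recorded on the AE CRF to include the event, date of onset, severity, frequency, seriousness, date of resolution", and the same sentence goes on to include relationship to the investigational product. For an AE lasting several days, section 10.2.2.1 already provides that "if an increase in severity level occurs, only the maximum level of severity will be documented", so counting at worst severity fits how the data are collected.

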12.2.8.2 SAFETY LABORATORY TESTS

Summary statistics of laboratory data will be presented for each visit by treatment group. Actual values and changes from baseline will be summarized using descriptive statistics. Shifts (below, within, and above the normal range) from Baseline will be summarized as well.

12.2.8.3 VITAL SIGNS

Summary statistics for vital signs will be presented for each visit by treatment group. Actual values and changes from baseline will be summarized using descriptive statistics.

12.2.8.4 ELECTROCARDIOGRAMS

Summary statistics for ECGs will be presented for each visit by treatment group. Actual values and changes from baseline will be summarized using descriptive statistics.

12.2.8.5 PHYSICAL EXAMINATION

Summary data of physical examination results will be provided by study visit by treatment.

12.2.8.6 ORTHOSTATIC BLOOD PRESSURE

The first blood pressure will be after the subject lies down for at least 5 minutes; the second blood pressure will be recorded after the subject stands for approximately 2 minutes. This will be repeated for a total of 3 times, approximately 15-20 minutes apart. The average of the three BP and pulse measurements will be used for comparison to all post-treatment measurements to minimize the impact of biological variability and to serve as a more reliable baseline orthostatic vital sign measurement. A drop in systolic blood pressure of ≥ 20 mmHg, or in diastolic blood pressure of ≥ 10 mmHg upon standing will be considered abnormal.

Orthostatic blood pressure will be summarized by time point with descriptive statistics. Change from baseline will be summarized by post-baseline time point, both with descriptive statistics and categorically.

12.2.8.7 COLUMBIA-SUICIDE SEVERITY RATING SCALE

The C-SSRS is a measure of suicidal ideation and behavior. The rating scale has 4 general categories: suicidal ideation, intensity of ideation, suicidal behavior, and actual attempts. All C-SSRS data will be listed.

12.2.8.8 IMPULSIVE COMPULSIVE DISORDERS IN PARKINSON'S DISEASE-RATING SCALE

The frequency and percentage of subjects with positive response ("rarely" or higher) for each disorder will be summarized by treatment group and visit. Furthermore, the total Impulsive Control Disorder score and the total QUIP-RS score will be summarized with descriptive statistics by treatment group and visit (both absolute values and changes from baseline).

13 INFORMED CONSENT, ETHICAL REVIEW, AND REGULATORY CONSIDERATIONS

13.1 INFORMED CONSENT

The Investigator is responsible for ensuring that the subject understands the potential risks and benefits of participating in the study, including answering any questions the subject may have throughout the study and sharing in a timely manner any new information that may be relevant to the subject's willingness to continue his or her participation in the trial.

The ICF will be used to explain the potential risks and benefits of study participation to the subject in simple terms before the subject is entered into the study, and to document that the subject is satisfied with his or her understanding of the risks and benefits of participating in the study and desires to participate in the study.

The Investigator is responsible for ensuring that informed consent is given by each subject. This includes obtaining the appropriate signatures and dates on the ICF prior to the performance of any protocol procedures and prior to the administration of investigational product.

13.2 ETHICAL REVIEW

The Sponsor or its representatives must approve all ICFs before they are submitted to the IRB and are used at investigative sites(s). All ICFs must be compliant with the ICH guideline on GCP.

Documentation of IRB approval of the protocol and the ICF must be provided to the Sponsor before the study may begin at the investigative site(s). The IRB(s) will review the protocol as required.

Any member of the IRB who is directly affiliated with this study as an Investigator or as site personnel must abstain from the IRB's vote on the approval of the protocol.

13.3 REGULATORY CONSIDERATIONS

This study will be conducted in accordance with:

1. consensus ethics principles derived from international ethics guidelines, including the Declaration of Helsinki and Council for International Organizations of Medical Sciences (CIOMS) International Ethical Guidelines
2. the ICH GCP Guideline [E6]
3. applicable laws and regulations.

The Sponsor certifies that this study is being conducted under an active US Investigational New Drug (IND) application.

Some of the obligations of the Sponsor will be assigned to a CRO.

13.3.1 INVESTIGATOR INFORMATION

Physicians with a specialty in neurology or physicians with experience or with medical site staff with experience in treating PD will participate as Investigators in this clinical trial.

13.3.2 PROTOCOL SIGNATURES

The Sponsor's responsible medical officer will approve the protocol, confirming that to the best of his or her knowledge, the protocol accurately describes the planned design and conduct of the study.

After reading the protocol, each principal Investigator will sign the protocol signature page and provide a copy of the signed page to a Sponsor representative.

15 APPENDICES

Appendix 1 Schedule of Assessments

Study Periods	SCRN	Treatment Period	Follow-up or Early Termination	Unscheduled visits ¹
Visit no.	1	2	3	
Study Day	-28 to 0	1	8 (± 1)	
Informed consent Form	X			
Demographic Data	X			
Medical History, including PD history	X			
Vital signs ²	X	X	X	X
Height and weight ³	X	X	X	X
Physical Exam	X		X	X
Neurological Exam	X		X	
Concomitant Medications	X	X	X	X
Columbia Suicide Severity Rating Scale (C-SSRS)-Baseline/Screening version	X			
Columbia Suicide Severity Rating Scale (C-SSRS)-Since last visit version		X	X	X
Montreal Cognitive Assessment (MoCA)	X			
Beck Depression Inventory-II	X			
QUIP-RS - Screening version	X			
QUIP-RS - Since last visit version		X	X	X
UPDRS Part III and dyskinesia rating in the OFF state	X ⁴	X ⁵		
UPDRS Part III and dyskinesia rating in the ON state	X ⁴	X ⁵		
Modified Hoehn and Yahr scale in the ON state	X			
12 lead ECG	X	X	X	X
Inclusion/exclusion criteria	X			

¹ Unscheduled visits may be conducted at any time for safety reasons and/or for any other reason.

² Vital signs include supine (at least 5 min) and standing (after approximately 2 min) BP and pulse rate, body temperature and body weight.

At Day 1, 3 sets each of supine and standing BP and pulse rate will be measured at least 15-20 minutes apart at pre-dose and will be measured once at 2, 4, 6, and 8 hours after dosing.

³ Height will be measured only once, at Screening. Body weight will be measured once per visit.

⁴ At screening, UPDRS Part III and dyskinesia rating should be done in the OFF and the ON state. This can be done in either the practically defined OFF state or after a subject wears OFF following a levodopa dose.

⁵ At Day 1, UPDRS Part III and dyskinesia rating will be conducted in the OFF state Pre-dose and every 30 minutes for 4 hours and then hourly for another 4 hours (or until subject turns OFF) following study drug administration. If the subject remains ON after 8 hours, they should be called the next morning to record the time they turned OFF, and the time they took their first regularly scheduled anti-parkinsonian medications after study drug, to a maximum of 24 hours.

BlackThorn Therapeutics, Inc.
Protocol NEP-PD-201 v4.0

Laboratory Evaluation	X		X	X
Urine drug screen	X			
Approval via Enrollment Authorization Committee (EAC)	X			
Randomization		X		
Study Drug administered		X		
Adverse Events		X	X	X
[REDACTED]		[REDACTED]		
Time to ON and duration of ON recorded		X		
Drug accountability		X		

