6 INVESTIGATIONAL PLAN

6.1 SUMMARY OF STUDY DESIGN

The study will consist of 3 sequential, ascending dose cohorts of 8 subjects each with a 6:2 randomization to BTRX-246040 or placebo. The planned dosing for each cohort will be 40, 80, and 120 mg. After enrollment of the first cohort has been completed, doses for subsequent cohorts may be modified based on review of the available data (safety, tolerability, efficacy, and PK) by an unblinded Dosing Review Committee (DRC). A similar review and determination of dosing for the subsequent cohort will be performed after completion of cohorts 1 and 2 and based on all data available from previous cohorts.

Following screening and acceptance by an Enrollment Authorization Committee, subjects in each cohort who meet entry criteria and sign an IRB approved informed consent, will present to the clinic on the morning of Day 1 in the practically defined OFF state (having withheld anti-parkinsonian medications after 10:00 PM the evening prior). Prior to dosing on Day 1, subjects will be randomized to either placebo or BTRX-246040. Subjects will then be dosed with study drug and UPDRS Part III motor response, dyskinesia and ON/OFF status will be assessed pre-dose and every 30 minutes for 4 hours and then hourly for 4 additional hours (i.e., 8 hours total post-dose). Subjects who turn ON following study drug administration and remain ON after 8 hours, should be called the next morning to record the time they turned OFF and the time they took their first regularly scheduled anti-parkinsonian medications after study drug, to a maximum of 24 hours. Subjects who turn ON following study drug administration and subsequently turn OFF may be administered their regularly scheduled levodopa dose and other anti-parkinsonian medications.

Subjects who

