8.2 VISIT 2: TREATMENT PERIOD (DAY 1)

For each cohort, subjects approved by the EAC for further participation in the study will return to the clinic within 28 days of the screening visit on the morning of Day 1, in the practically defined OFF state (having not taken any anti-PD medications since 10 PM the evening before).

Subjects will come to clinic in a fasted state and will be administered a standard low protein breakfast. Subjects will be randomized to either BTRX-246040 or placebo.

In the clinic, subjects determined to be in the OFF state by the Investigator will be dosed with study drug and UPDRS Part III motor response and dyskinesia rating, and ON/OFF status will be assessed pre-dose and every 30 minutes post-dose for 4 hours, and then hourly for an additional 4 hours (i.e., 8 hours total post-dose). Time to ON and duration of ON, if applicable, will also be recorded.

Subjects who reach and remain in the ON state for 8 hours may resume their regularly scheduled anti-parkinsonian medications 8 hours post-dosing. Subjects should remain on study drug until they experience an OFF episode after a full ON for 8 hours. However, if after 4 hours post study drug dosing, a subject's motor symptoms are severe and not responsive to study drug, the subject's regularly scheduled levodopa dose and other anti-parkinsonian medications may be administered, if deemed necessary based on the judgment of the investigator. All subjects whether they are administered their regularly scheduled anti-parkinsonian medications or not, will continue with study procedures until the end of the observation period of 8 hours.

The following assessments will be completed on Day 1 - see the Schedule of Assessments ([Appendix 1](#)) for details:

1. Collection of concomitant medications

2. Vital Signs: (BP and pulse both supine and standing, respiratory rate, temperature) and weight. Three sets each of supine and standing BP and pulse rate will be measured at least 15-20 minutes apart at pre-dose and will be measured once at 2, 4, 6, and 8 hours after dosing
3. C-SSRS – since last visit version
4. QUIP-RS – since last visit version
5. 12-lead ECG pre-dose and 1 hour after study drug administration.
6. Randomization via IWRS

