7. UPDRS Part III and dyskinesia rating in the OFF state pre-dose and every 30 minutes for 4 hours and then hourly for another 4 hours (i.e., 8 hours following study drug administration). If the subject remains ON after 8 hours, they should be called the next morning to record the time they turned OFF, and the time they took their first regularly scheduled anti-parkinsonian medications after study drug, to a maximum of 24 hours.
8. Administration of Study drug
9. Time to ON and duration of ON following study drug administration.

11. Drug accountability.

12. Collection of AEs.

Subjects will be discharged from the clinic and instructed to return to the clinic 7 days later (Day 8 ±1).

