10.1 EFFICACY MEASURES

10.1.1 UNIFIED PARKINSON'S DISEASE RATING SCALE

The UPDRS is well-established and the most widely used assessment to quantify the signs and symptoms of PD (Fahn, Elton, & Committee, 1987). The total UPDRS consists of 4 parts which assess the following:

1. Mentation, behavior and mood
2. Activities of Daily Living (ADL)
3. Motor function
4. Complications of therapy

Only Part III will be utilized in this trial. The UPDRS Part III is a 14-item rating scale, which consists of the motor examination. Each item is scored from 0 (Normal) to 4 (Most severe). The UPDRS Part III scale should only be administered by a rater who has adequate experience with subjects with PD and should be a trained neurologist or other trained research staff with experience in conducting the UPDRS. All attempts should be made to ensure that the same trained research staff member performs the UPDRS part III for a given subject.

An additional single item to rate dyskinesia is added to the scale and is rated from 0 (No dyskinesia) to 4 (Severe dyskinesia: maximal amplitude and present during most of the exam).

The UPDRS and dyskinesia rating will be conducted as indicated in the Schedule of Assessments (Appendix 1).

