12.2.7.3 SECONDARY EFFICACY ANALYSES

The secondary endpoints consist of the following:

- Duration of ON time on Day 1
- Percentage of subjects that turn ON on Day 1
- Time to ON on Day 1
- Area under the curve for UPDRS Part III during the 8 hours of assessment on Day 1
- Change from pre-dose dyskinesia rating (from the UPDRS Part III motor response and dyskinesia assessment)

For continuous variables, descriptive statistics (n, mean, SD, median, minimum, and maximum) will be provided for actual values and changes from baseline to each time point. For categorical variables, subject counts and percentages will be provided. Summaries will be presented by treatment group. Graphical displays will be created as appropriate, including for the UPDRS by time point.

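### Appendix 1 footnote 5 lets Day 1 motor ratings stop when a subject turns OFF, against the fixed 8 hours of sections 6.1 and 8.2, so the 8-hour AUC would be cut short only in subjects who turned ON and then OFF

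*Protocol*

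**What the plan says.** The protocol gives the Day 1 rating schedule for UPDRS Part III and dyskinesia in several places, and they do not agree on when rating ends.

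- Appendix 1, footnote 5: "every 30 minutes for 4 hours and then hourly for another 4 hours (or until subject turns OFF) following study drug administration".
- Section 8.2, item 7: "every 30 minutes for 4 hours and then hourly for another 4 hours (i.e., 8 hours following study drug administration".
- Section 8.2, text above the list: all subjects, whether or not they have taken their usual anti-parkinsonian medication, "will continue with study procedures until the end of the observation period of 8 hours". The synopsis and section 6.1 state the same rule.

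Section 8.2 refers the reader to Appendix 1 for details, and section 10.1.1 defers to it outright: "The UPDRS and dyskinesia rating will be conducted as indicated in the Schedule of Assessments". The protocol does not say which text prevails.

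The endpoint that needs the full schedule is the secondary endpoint in section 12.2.7.3: "Area under the curve for UPDRS Part III during the 8 hours of assessment on Day 1". The change in dyskinesia rating, also secondary, is summarised by time point.

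**The concern.** Nearly identical sentences carry different stopping rules. One fixes the end at 8 hours; the other lets it come earlier, at a moment set by the subject's own response.

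That makes the loss selective. According to section 8.2, "subjects determined to be in the OFF state by the Investigator will be dosed with study drug". A subject who never turns ON cannot turn OFF and is rated to 8 hours, and a subject still ON at 8 hours also loses nothing. Only subjects who turn ON and then OFF within the window are cut short. The ratings would be missing because of the outcome being measured, and no later analysis plan can recover ratings that were never taken.

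The sign of the error is not known in advance. Section 6.1 says: "Subjects who turn ON following study drug administration and subsequently turn OFF may be administered their regularly scheduled levodopa dose". The unrecorded hours may therefore hold poor scores (no medication) or good ones (after medication).

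**Working it through.** **Can the texts be read together?** Three readings of the parenthesis in footnote 5 were tried.

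- It extends clinic rating beyond 8 hours. This fails, because the footnote's next sentence sends those subjects to a telephone call: "If the subject remains ON after 8 hours, they should be called the next morning to record the time they turned OFF".
- It qualifies the whole schedule (broad reading). Rating stops at the first OFF at any time after an ON.
- It qualifies only the hourly phase from 4 to 8 hours (narrow reading). Up to 4 ratings are lost.

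Both workable readings contradict section 8.2, item 7.

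**Ratings lost.** The schedule has 12 post-dose ratings: 0.5, 1, 1.5, 2, 2.5, 3, 3.5, 4, 5, 6, 7 and 8 h. On the broad reading, with the last rating taken at the OFF:

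| Rated OFF at | Ratings lost of 12 |
|---|---|
| 2.5 h | 7 |
| 3 h | 6 |
| 4 h | 4 |
| 5 h | 3 |
| 6 h | 2 |
| 7 h | 1 |
| never ON, or still ON at 8 h | 0 |

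**Effect on the AUC.** The protocol gives no expected scores and no AUC to reproduce. The scores here are assumptions: OFF 40, ON 25, ON from 1 h. AUC is by the trapezoidal rule, the sum of interval length times the mean of the two end scores. A constant score of 40 gives 8 × 40 = 320 point-hours.

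*Example 1: rated OFF at 5 h (both readings stop at 5 h; 9 of 12 ratings taken).*

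- Observed 0-5 h: 20 + 16.25 + 75 + 32.5 = 143.75; average 143.75/5 = 28.75.
- Full 0-8 h, no medication: 143.75 + 3 × 40 = 263.75; average 32.97.
- Full 0-8 h, usual medication giving 25 from 6 h: 143.75 + 32.5 + 50 = 226.25; average 28.28.
- Difference from 320: 56.25 or 93.75.
- Error of the observed average: 28.75 - 32.97 = -4.2, or 28.75 - 28.28 = +0.5 points.

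*Example 2: rated OFF at 3 h.*

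- Broad reading: 6 of 12 ratings; 0-3 h = 20 + 16.25 + 37.5 + 16.25 = 90; average 30.0.
- Narrow reading: 8 of 12 ratings; 0-4 h = 90 + 40 = 130; average 32.5.
- Full 0-8 h, no medication: 130 + 160 = 290; average 36.25.
- Full 0-8 h, 25 from 5 h after medication: 130 + 32.5 + 75 = 237.5; average 29.69.

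**Effect on a cohort.** In Example 1 the unrecorded hours are worth 263.75 - 226.25 = 37.5 point-hours. With six active subjects per cohort, one such subject moves the active mean by 37.5/6 = 6.25 point-hours.

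**Effect on the primary endpoint.** The lowest post-dose score is 25 in every case, so the maximal change is 25 - 40 = -15 with or without the cut.

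**The case against.** The strongest reply concerns weight. The 8-hour schedule appears repeatedly in the body text, three places add the rule that all subjects continue to 8 hours, and section 8.2, item 7, states the timing in full. Only section 10.1.1 leaves the timing wholly to the appendix, so most sites might rate to 8 hours anyway. This stands as a point about likelihood. It does not remove the contradiction, and the schedule table is a place where sites look.

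The illustration is also open to challenge. Its scores are assumed, and the reference of 320 supposes a never-ON subject who stays unmedicated. The protocol allows usual medication after 4 hours in severe non-responders. With 25 from 5 h, such a subject has 160 + 32.5 + 75 = 267.5, a shift of 52.5 that has nothing to do with footnote 5. So even a complete 8-hour AUC can contain the effect of usual medication. This stands too: the figures show the mechanism, not an expected bias, and removing the parenthesis does not by itself give an AUC of study drug alone.

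A further reply is that recording dose times is a CRF matter, because medications taken after study drug are already listed on the CRF. Partly so. However, the protocol explicitly asks for the time of the first usual dose only in subjects still ON after 8 hours, and the subjects at issue here are the others. How ratings after medication are analysed may properly be left to the SAP.

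Finally, the analysis is descriptive and the AUC is secondary. That limits the importance of the point but not its correctness.

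**Conclusion.** The concern holds. Footnote 5 contradicts section 8.2, item 7, and the all-subjects rule in the synopsis and sections 6.1 and 8.2, on either workable reading. If a site follows it, a subject who turns ON and then OFF before 8 hours loses between 1 and 7 of the 12 post-dose ratings in the cases tabulated, while never-ON subjects and those still ON at 8 hours lose none because of it. The 8-hour AUC and the later dyskinesia time points would be incomplete in a response-dependent way.

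The contradiction rests on the text alone. The AUC sizes rest on assumed scores, and the number of subjects affected cannot be estimated from the protocol. The direction of bias is open, and the primary endpoint is little affected because the best score before medication normally precedes the OFF. The point should be corrected, but it does not threaten the study.

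**What to change.** Delete the stop-at-OFF parenthesis from footnote 5 so that it matches section 8.2, item 7. Every subject then has 13 scheduled ratings (pre-dose plus 12) whatever the ON/OFF status, and the 8-hour AUC can be calculated for all.

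Also record the clock time of any anti-parkinsonian dose taken within the 8 hours, so that ratings made after it can be identified and kept apart from the study-drug effect in the maximal change and AUC. This concerns recording only; it leaves the rules on when usual medication may be given untouched.

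The cost is one phrase in the appendix, one recorded time, and a few more ratings (3 to 6 in the examples) in subjects who are already on site to 8 hours for orthostatic vital signs. No visit is added.
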